9. RISKS TO SUBJECTS

Based on inclusion criteria of suicide crisis and the psychiatric inpatient recruitment setting, participants in this study are likely to have some increased risk for suicidal behavior (6, 33, 35). Thus, subjects must consent to remain in outpatient mental health care during the study. Consistent with URMC policy 5.4 (Patient Safety Plans Policy), a safety plan will be created for all inpatients enrolled in the study and reviewed by the subject's clinician prior to discharge. The plan includes a list of resources that the subject can call on when in need or at increased risk. If the subject declines to complete the safety plan, the clinician will make a note of this declination and provide crisis/safety resources. Finally, a copy of the safety plan is provided to the patient (subject), (and family/support person, as appropriate), and bookmarked in the patient's chart. There is a risk that the assessment and intervention may cause stress or discomfort. Subjects are informed of this during the consent process and given the option to decline to answer questions or discuss topics they do not wish to discuss. They can take breaks or stop a clinical assessment at any time. Research staff will promote subject comfort, including appropriate pacing of assessments and interventions, providing breaks, and discontinuing any clinical assessment when requested by a subject or it is clinically indicated.

The tolerability and safety of home-based tDCS were assessed over 6,779 sessions from six clinical trials, with daily session, varying from 10 to 60 applications. The authors reported no serious adverse events, a similar proportion of tingling (68%), itching (41%), and warmth sensation (42%) between active and sham groups, and no participant discontinuation due to lack of tolerability (39). As described in "Study procedures," a tolerability test will be performed as part of the orientation session to verify if the subject can tolerate the electric current established in the protocol. Subjects will be informed that they can stop an RS-tDCS session anytime. During the RS-tDCS session, the stimulation will be stopped if the subject reports a sensation of pain rated as an intensity of 7 or above on a 1-10 scale (46). If the subject reports any event of critical concern related since the last RS-tDCS session, the next RS-tDCS session will not start until clear that the event is not stimulation-related. All devices function only after the inclusion of a unlock code for one-time use. The unlock codes for one-time use allow the device to function only once a day, just after the inclusion of the code, with the level of electric current and duration of the session determined by the protocol, both (electric current level and duration of the session) pre-programmed on the device before it is delivered to the subject.

Imminent risk of suicide, for the purposes of this study, refers to a subject who is currently 1) thinking about suicide; 2) preparing for suicide and/or having planned for suicide; and has 3) some intent to act on the suicide plan within the very near future (generally 48 hours).

This may differ for each case and therefore, clinical judgment along with timely consultation are needed for determination of imminence. Thus, to assess imminent risk of suicide, the following procedures will be undertaken:

a) at the baseline assessment in the hospital:

- after the C-SSRS assessment, research staff will ask the subject if there is current active suicidal ideation with plan and intent. If the subject reports current active suicidal ideation plan and intent at the baseline, research staff will inform the subject that they need to communicate this information (about the active suicidal ideation with specific plan and intent) to the unit staff in charge of the patient due to safety concerns.
- research staff will also communicate with the unit staff in case of any concerns about the subject during the baseline assessment.
- For this assessment, the following questions will be added, and the research staff must provide the answers ("yes" or "no"): "Active ideation with plan and intent *currently*?"; "Are you otherwise concerned about the patient at all?"

b) at the RS-tDCS sessions:

- after the C-SSRS screening version assessment, research staff will ask the subject if there is current active suicidal ideation with plan and intent. If the subject reports current active suicidal ideation plan and intent, research staff will inform the subject that they need to communicate this information (about the active suicidal ideation with specific plan and intent) to a licensed clinician from the research team to discuss the need for a specialized assessment.
- research staff will also communicate the licensed clinician in case of any concerns about the subject during the RS-tDCS sessions.
- For this assessment, the following questions will be added, and the research staff must provide the answers ("yes" or "no"): "Active ideation with plan and intent *currently*?"; "Are you otherwise concerned about the patient at all?"

c) at the clinical assessments (day 14, day 30, and day 60 from the first RS-tDCS session):

- after the C-SSRS assessment, research staff will ask the subject if there is current active suicidal ideation with plan and intent. If the subject reports current active suicidal ideation plan and intent, research staff will inform the subject that they need to communicate this information (about the active suicidal ideation with specific plan and intent) to a licensed clinician from the research team to discuss the need for a specialized assessment.
- research staff will also communicate the licensed clinician in case of any concerns about the subject during the follow-up assessments.
- For this assessment, the following questions will be added, and the research staff must provide the answers ("yes" or "no"): "Active ideation with plan and intent currently?"; "Are you otherwise concerned about the patient at all?"

The licensed clinician will follow the best policies and procedures of URMC and applicable state law for providing resources and determining if emergency evaluation is required. At minimum, the licensed clinician will:

- Advise the subject about emergency contact number
- Ask the subject to review the steps of the discharge safety plan from the inpatient unit or

the safety planning the subject may have with outpatient provider

- Inquire about and reinforce the need to attend existing appointments
- Verify the subject's understanding by asking what steps they will take if their condition deteriorates

There is a risk of loss of confidentiality if safety concerns are discovered (i.e., suicidal intent). Subjects are informed during the consent process that study staff will break confidentiality if subjects are assessed to be at risk for suicidal behavior and take appropriate actions, including alerting the clinical care provider, referring for emergency evaluation, or other actions such as calling 911. Additionally, if we witness or the subject discloses information regarding potential serious harm to others, including child abuse or neglect, abuse of a disabled adult, or elder abuse, we will also contact the appropriate authorities.

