7. The level of side effects will be assessed at the end of each session on a 0 (not at all) to 10 (highest degree) scale used by Ahn et al. (2019) (37), which includes the following symptoms: 1. Itching; 2. Burning; 3. Headache; 4. Fatigue; 5. Nervousness; 6. Dizziness; 7. Difficulty concentrating. The total score is the sum of the 7 items, varying from 0 to 70. Higher scores indicate higher levels of side effects.

8. Treatment emergent event review: after each RS-tDCS session and clinical assessment, subjects will be asked "Have you had any new symptoms, new medical conditions or been started on new medication/treatment since we last saw you?". This information will help research staff to judge about potential adverse events related to the trial. In addition, changes in treatment will help researchers to account for them in data analysis and the study's results interpretation.

4.1. **STUDY INTERVENTION**

The study intervention is tDCS treatments delivered by the Soterix Medical mini-CT device (https://soterixmedical.com/research/remote/mini-CT). The device is a nonsignificant risk (NSR) device study because it does not meet the definition of a significant risk device under §812.3 (m) of the investigational device exemptions (IDE) regulation (21 CFR §812)

(https://www.accessdata.fda.gov/scripts/cdrh/cfdocs/cfcfr/CFRSearch.cfm?fr=812.3).

The Soterix Medical mini-CT device for the RS-tDCS includes: (1) 1 x 1 mini-CT tDCS device; (2) SNAPstrap headgear, a "cap"-like placement for simple positioning and uniform electrode placement; (3) SNAPpads (individually-packaged pre-moistened sponge), and snap connectors (Figure 1) (39).

[figure not shown]

Figure 1. Remotely supervised (RS-tDCS) Equipment. (1) 1 x 1 mini-CT tDCS device; (2) SNAPstrap headgear: "cap"-like placement for simple positioning and uniform electrode placement; (2a) markers for guidance in placement; (2b) electrode polarity labeling with fixed wiring. (3) SNAPpad: (3a) individually-packaged pre-moistened sponge; perforated packaging for easy opening; (3b) snap connectors. (adapted from Pilloni, G., A. et al., Brain Stimul 15(3): 707-716, http://creativecommons.org/licenses/by-nc-nd/4.0/, DOI: 10.1016/j.brs.2022.04.014). The figure at the bottom simulates an RS-tDCS session.

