8. STUDY PROCEDURES

The pre-screening will be carried out through the electronic hospital medical record to identify potential subjects. Once the potential subject is identified, research staff will visit the unit where the patient is receiving treatment (inpatient unit or CPEP) and talk with unit staff in person, providing information about the study. Then, the research staff will ask unit staff to determine the most appropriate time for the research staff to meet with the patient based on knowledge of patient status and needs.

[figure not shown]
After screening and signing consent, the research study staff will collect demographic and general medical history data, apply the clinical questionnaires, and conduct the orientation tDCS session as part of the in-person baseline assessment (Table 1 and Figure 3). This demographic, general medical history, and clinical data will be collected and stored in the REDCap through a tablet or another portable electronic device. Per subject need/request, research study staff reads aloud instructions and questions while subjects hold the tablet to record their answers. If the REDCap site is down or malfunctioning, screening, consent, and questionnaires are completed on paper and later entered into REDCap.

The orientation session includes presenting the Soterix Medical mini-CT device to the subject to show how to turn it on/off, how to insert the device unlock codes for one-time use, how to correctly adjust the SNAPstrap headgear, and answer any questions they may have. As part of the orientation session, research staff will also conduct a 90-s tolerability test, with 2.0 mA as the starting point (electrical current intensity of the study protocol). During this test, the current intensity is ramped up to 2.0 mA and the subject will receive the stimulation for 90 seconds. The tolerability will be determined by subject rating below 7 on the 0-10 Visual Analogue Scale (VAS) of pain. If the subject finds the target tDCS dose intolerable (i.e., VAS 7 or higher), subjects will have the option of another test, with the amperage dose decreased by 0.5 mA (i.e., to 1.5 mA). If this lower amperage is also intolerable, the subject will be excluded from the study (39, 46). Thus, the orientation session aims to 1) familiarize the subject with the

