device, how to turn it on/off, and insert the unlock codes for one-time use; 2) to assess if the subject tolerates the protocol electric current through the tolerability test; 3) answer any questions the subjects may have. As the Soterix Medical mini-CT device will be with the subjects during the RS-tDCS sessions, subjects will be asked to sign an IRB-approved device loan agreement at the baseline.

Clinical questionnaires will be re-administered at day 14 [+ 7 days], day 30 [+ 7 days], and day 60 [+ 10 days] from the first RS-tDCS session session15 (Figure 3). While we aim to reach subjects on the phone for follow-up, research staff may email or text subjects to schedule the RS-tDCS sessions and clinical assessments. Subject identifying information and protected health information (PHI) is not exchanged in the text messages themselves. Detailed information about text messaging is included under the "Privacy and Confidentiality of Subjects and Research Data" section. Security risks associated with text messaging are described in detail during consent.

After baseline assessment, research staff not involved in the RS-tDCS supervisions and clinical assessments will randomize the subject to active or sham control group and set up the device condition (active or sham), program the intensity for the active condition (either 2.0 mA or 1.5 mA, according to the tolerability test) and duration (30 minutes) of each session, and get the device unlock codes for one-time use to be provided by the research staff to the subject immediately before each session. The discharge day will be tracked daily by the research staff through the electronic hospital medical record. Once the subject is discharged, research staff will deliver the RS-tDCS device by mail to the subject's address in a pre-paid FedEx package to send it back and contact the subject once the device has arrived at their home (by using the mail tracking number) to schedule the first RS-tDCS session.

*device set up for the condition (active or sham), and locked (unlock codes for one-time use will be provided before each session); **day 1 being the first RS-tDCS session and no sessions on weekends. CPEP: Comprehensive Psychiatric Emergency Program; DLPFC: dorsolateral prefrontal cortex; RS-tDCS: remotely supervised transcranial direct current stimulation.

RS-tDCS sessions:

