Research staff with training in using home-based tDCS by the Soterix Medical will meet with the subject via HIPAA-compliant videoconference previously scheduled. Subjects will be encouraged to find a distraction-free setting to complete treatment sessions. After guiding the subject with the proper adjustment of the SNAPstrap headgear and turning on the 1 x 1 Mini-CT device, research staff will provide the device unlock codes for one-time use to the subject. All ten device unlock codes for one-time use (one for each tDCS session) are obtained previously, just after the device is programmed to active or sham. The device unlock codes for one-time use allow the device to function only once a day, just after the inclusion of the code, with the level of electric current and duration of the session determined by the protocol, both (electric current level and duration of the session) pre-programmed on the device before it is delivered to the subject. Thus, the subject cannot alter the electric current level, the duration of the session, or use the device more than once a day. After each RS-tDCS session, research staff will apply the side effects questionnaire, review the subject's current treatment ("treatment review"), ask about any new or updated mental or physical symptoms since the last assessment (adverse events review), and apply the C-SSRS - screening version (C-SSRS SV) as part of the risk assessment (please, see more details on item "9. RISK TO SUBJECTS"). After the last RS-tDCS session (the tenth session), research staff will apply the feasibility questionnaire and blinding assessment. (Table 1). To assess blinding, the subjects will be asked the following question, "What treatment do you believe you have received??"(47). There will be three possible answers: 1) "active-tDCS"; 2)

"sham-tDCS" or 3) "Don't know". If the answer is "Don't know", research staff will ask "Would you be willing to provide your best guess about the treatment you received?", and could choose from two possible replies: 1) active-tDCS; 2) sham-tDCS (47, 48). We will use the Bang Blinding Index, which varies from -1 to +1, being 1 complete lack of blinding, +1 the opposite guessing, and 0 being related to perfect blinding (48). After the tenth session, the subject will be asked to send back the equipment in the pre-paid mail package to send it back.

Clinical assessments:

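### Within each session the event and new-treatment questions follow stimulation, but the hold must act before it: a minor gap that is cheap to close

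*Combined protocol and SAP*

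**What the plan says.** - **The hold (Section 9).** "If the subject reports any event of critical concern related since the last RS-tDCS session, the next RS-tDCS session will not start" until it is clear that stimulation was not the cause. The rule turns on the subject reporting the event. It does not say when or how the subject is asked.
- **Before stimulation (Section 8, RS-tDCS sessions).** Staff meet the subject by videoconference, help with the headgear and have the device switched on. Then "research staff will provide the device unlock codes for one-time use to the subject". No event or treatment question is listed among these steps.
- **After stimulation (Section 8).** "After each RS-tDCS session, research staff will apply the side effects questionnaire". In the same block they review current treatment, "ask about any new or updated mental or physical symptoms since the last assessment (adverse events review"), and give the C-SSRS screening version.
- **Outcome 8 (Section 4).** The order is the same: "after each RS-tDCS session and clinical assessment, subjects will be asked" about new symptoms, conditions and treatments. Table 1 marks this review at S1 to S10 and at C14, C30 and C60, without an order inside a session.
- **Removal (Section 13).** A subject who starts ECT or TMS at any time in the trial is removed.
- **Calendar.** Section 8 has "day 1 being the first RS-tDCS session and no sessions on weekends". Section 4 puts the assessments 14, 30 and 60 days after the first session, and counts sessions completed within three weeks of receiving the device.

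**The concern.** The hold is a decision taken before a stimulation, but the question that would inform it is scheduled after that stimulation. Events during or just after session k are well covered: that session's own review asks about them in time to hold session k+1. The gap is for events that begin after that review and before session k+1. Followed as written, the schedule first asks about these once session k+1 has been delivered, unless the subject mentions them or staff ask on their own initiative. The same applies to a new course of ECT or TMS, which should end participation. What is at stake is one further 30-minute session in a recently discharged subject at home, when the plan's own rule would have stopped it.

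**Working it through.** The plan gives no figure on this point, so there is none to reproduce. The check is on order and calendar, followed by a rough size.

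**1. Can the day 14 assessment act as a gate?** Ten consecutive weekday sessions starting on a Monday end on study day 12, which is 11 days after the first session. Starting on any day from Tuesday to Friday, they end on study day 14, which is 13 days after it. C14 is due 14 days after the first session or up to 7 days later, so on the nominal calendar it follows session 10. Three weeks hold about 3 × 5 = 15 weekdays, so sessions can slip. If they do, C14 may by chance precede a remaining session. C30 and C60 come too late to matter.

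**2. How late is the question?** Take an event that starts between sessions k and k+1. It is first asked about after session k+1, so a hold prompted by a scheduled question can first stop session k+2.
- Ten sessions give 9 intervals.
- For k = 1 to 8, session k+2 exists, so the hold is one session late.
- For k = 9, no session is left to hold.

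**3. How long are the intervals?** A Monday start spans one weekend and any other start spans two. So 8 or 7 intervals last about 1 day, and 1 or 2 last about 3 days.

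**4. How many intervals?** Twenty subjects randomized 1:1 give about 10 active subjects.
- All complete 10 sessions: 10 × 9 = 90 intervals.
- All stop at 5 sessions: 10 × 4 = 40 intervals.

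These are intervals without a prior scheduled question. They are not harms.

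**5. How many serious events might that involve?** The documents give no event rate for this trial. Section 9 cites no serious adverse events in 6,779 home sessions of other trials.
- 95% upper bound by the rule of three: 3 / 6,779 = 0.0443% per session.
- Exact: 1 − 0.05^(1/6,779) = 0.0442%.
- Over 90 intervals: 90 × 0.000443 = 0.040 events.
- Over 40 intervals: 40 × 0.000443 = 0.018 events.

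This assigns the whole per-session bound to between-session onset and assumes that no subject volunteers the event, so in those respects it is high. In other respects it may be low. It pools active and sham sessions, comes from other populations, and covers serious events only, whereas the hold applies to events of critical concern, a term the plan does not define and which may be wider.

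**The case against.** The strongest reply is that the control already exists. Trained staff are on a live call before every stimulation and release a one-time code, so a subject with a problem can say so and staff can stop. Section 9 also requires staff to raise any concern during the sessions with a licensed clinician, and that duty is not confined to the time after stimulation. The pain stop rule likewise relies on the subject speaking up. The session form is not among the documents and might contain a prompt. The removal rule for ECT and TMS sets no pre-session check, and current ECT or TMS is already excluded at entry.

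Much of this stands, and it is why the point is minor. What remains is that the written procedure leaves the pre-session step to spontaneous mention or staff initiative, although the plan already has a suitable question and a natural control point. It is also fair to say that the remedy leaves critical concern undefined and does not itself ask about suicidal thoughts. The separate suicide-risk check after each session continues as written.

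A reader might infer three stronger things that the documents do not support:
- **That event questions occur only after stimulation.** They also occur at C14, C30 and C60.
- **That between-session events are lost.** The post-session review looks back to the previous assessment, so they are still asked about. Neither their recording nor the primary outcome is affected.
- **That the time from baseline to session 1 is an important gap.** The hold does not reach back that far, but the only stimulation in that time is the supervised tolerability test, in which "the current intensity is ramped up to 2.0 mA and the subject will receive the stimulation for 90 seconds", with one optional repeat at 1.5 mA. Extending the wording would add little.

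**Conclusion.** The point holds as a minor safety improvement. Inside each session the order of questions does not serve the hold in Section 9 or the removal rule in Section 13. A between-session event or new ECT or TMS course that is neither volunteered nor elicited on the call is first asked about one stimulation late, or after the last session if it arises between sessions 9 and 10. The documents do not support a claim of frequent or likely harm. On the one available figure, the expected number of serious events is at most about 0.04 over the trial, provided that the bound from other trials carries over. The count of intervals assumes 10 active subjects, and their lengths assume consecutive weekday sessions. The case for change rests on the mismatch in the text and the very low cost of removing it.

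**What to change.** In Section 8 (RS-tDCS sessions) and in outcome 8 of Section 4, add that the existing treatment-emergent event question is also asked at the start of each videoconference, before the unlock code is released. State that the Section 9 hold and the Section 13 removal rule apply to the answer. Keep the post-session side-effects questionnaire, treatment and event reviews and C-SSRS screening version unchanged, so that symptoms arising during stimulation are still asked about. Table 1 needs no edit, because it already marks the review at S1 to S10 and gives no order within a session.

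**Cost.** Protocol wording and one line on the session form, with the same staff and the same call. At an assumed 1 minute per call, 20 subjects × 10 calls = 200 calls, or at most 200 minutes over the trial. The real downside is an occasional delayed session. The three-week window leaves about 15 − 10 = 5 spare weekdays, less the time taken to schedule session 1. Sample size and primary analysis do not change.
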